9.3.2 Safety and effectiveness outcomes

For each outcome, potential cases will be identified using diagnostic Read codes ([Annex 3](#)) and, where appropriate, computerized patient profiles (including any free text comments) will be reviewed with all identifying information removed. Diagnostic confirmation using patients' original medical records will be performed where possible. When required, information contained in HES among the subset of practices linked to THIN, will be used.

For the purpose of this study, clinically relevant bleedings will be defined as bleedings leading to hospital admission or referrals to a specialist. This restriction is needed to minimize differential misclassification caused by the variability in patients' behavior in seeking care for less severe bleedings. Similarly, the physicians' attitude towards recording these events may differ between new drugs and standard of care. The consequence of restricting to bleedings identified through hospitalization or referrals is that bleedings leading to death before contact with a health care professional or hospital admission might be missed. It is assumed that the number of bleeding events missed due to this restriction is small. Nevertheless, the magnitude and impact of this restriction will be assessed in another study of this PASS program (Swedish Record-linkage study).

9.3.2.1 Occurrence of intracranial haemorrhage, gastrointestinal bleeding and urogenital bleeding: case definitions

Intracranial haemorrhage (Annex 3, Table 4)

Cases of intracranial haemorrhage will be identified in patients referred to a specialist or admitted to hospital that meet the criteria for one of the three following categories:

- incident cases of intracerebral haemorrhage recorded following or in association with computed tomography, magnetic resonance imaging (MRI) or X-ray angiography, or an appropriate therapeutic procedure.
- incident cases of subarachnoid haemorrhage recorded following computed tomography, MRI, X-ray angiography or lumbar puncture, or an appropriate therapeutic procedure.
- incident cases of epidural, dural, subdural and arachnoid haemorrhage recorded following computed tomography, MRI, X-ray angiography or lumbar puncture, or an appropriate therapeutic procedure.

Gastrointestinal bleeding (Annex 3, Table 5)

A patient will have to meet the following criteria to be considered a case of gastrointestinal bleeding:

- the specific site of bleeding originating in the upper or lower gastrointestinal tract or, more specifically, in the oesophagus, stomach, duodenum, jejunum, ileum, colon or rectum.
- for upper gastrointestinal bleeding, the lesion type being erosion, gastritis, duodenitis or peptic (gastric or duodenal) ulcer.
- the lesion type being NOT related to cancer.
- the patient having been referred to a specialist or admitted to hospital.

Urogenital bleeding (Annex 3, Table 6)

A patient will have to meet both of the following criteria to be considered a case of urogenital bleeding:

- the specific site of bleeding originating in the urogenital tract.
- the patient having been referred to a specialist or admitted to hospital.

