9.4 Data sources

The data source for this study will be The Health Improvement Network (THIN) database in the UK. THIN includes information on over 3 million patients (approximately 5% of the UK population) that is systematically recorded by participating PCPs as part of their routine patient care and is anonymized and sent to THIN for use in research projects. The computerized information includes demographics, details of PCP visits, referrals to specialists and hospital admissions (including diagnostic and treatment information), results of laboratory tests and a free-text section. Prescriptions issued by the PCP are recorded electronically and the indication can be ascertained by reviewing the patient's clinical history. The Read classification is used to code specific diagnoses as reasons for each consultation (O'Neil, Payne et al. 1995; Stuart-Buttle, Read et al. 1996), and a drug dictionary based on data from the MULTILEX classification is used to record prescriptions (First Data Bank 2014).

Recently, a number of practices included in THIN database have been linked to the HES database. HES is a data warehouse containing details of all admissions, outpatient appointments and Accident and Emergency attendances at NHS hospitals in England.

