9.5 Study Size

All patients enrolled in THIN and meeting the inclusion criteria will be included. The size of the population receiving rivaroxaban will be dependent on market uptake across the indications of interest (DVT/PE treatment, ACS and SPAF).

According to a preliminary sample size calculation, based on an incidence of haemorrhagic stroke in warfarin-treated patients of 5 per 1000 person-years, 12,000 rivaroxaban-treated patient-years and 48,000 warfarin-treated patient-years would be required to exclude a 50% increased risk of haemorrhagic stroke in rivaroxaban-treated patients compared with warfarin-treated patients with a power of 80%.

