9.7.1 Patient characteristics and drug utilization

The patient populations will be described according to the descriptive variables mentioned in Section 9.3.1. overall and stratified by indication (VTE prevention, DVT/PE treatment, SPAF, ACS, other), naïve or non-naïve status, and switching status.

The baseline risk of being dispensed one of the co-medications or presenting with one of the comorbidities prior to the index date will be assessed by computing the odds ratio of being prescribed that drug or presenting with that comorbidity among first-time users of rivaroxaban compared with first-time users of standard of care. Age- and sex-adjusted odds ratios and 95% confidence intervals for the descriptive variables ([Section 9.3.1](#)), will be computed using logistic regression models both overall and stratified by indication and by naïve or non-naïve status, and switching status.

Manual review of patient profiles will be used to ascertain as accurately as possible exposure time in a random sample of warfarin users. In addition, INR measurements will be used as a proxy for warfarin exposure, which is more valid measure of true exposure to warfarin.

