9.8 Quality control

For each outcome, potential cases will be identified using diagnostic Read codes ([Annex 3](#)) and, where appropriate, computerized patient profiles (including any free text comments) will be reviewed with all identifying information removed. Diagnostic confirmation using the patients' original medical records will be performed where possible by means of sending a questionnaire to the PCP. When required, we will use the information contained in HES among the subset of THIN practices linked to THIN.

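### Exposure is not masked before potential cases are reviewed, so case acceptance could differ between the rivaroxaban and comparator cohorts

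*Protocol*

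**What the plan says.** Protocol Section 9.3.2 finds potential cases by the Read codes in Annex 3. It then provides, where suitable, that "computerized patient profiles (including any free text comments) will be reviewed with all identifying information removed". Section 9.8 repeats this and adds: "Diagnostic confirmation using the patients' original medical records will be performed where possible by means of sending a questionnaire to the PCP". HES data may be used in linked practices. Identity is the only thing either section says is removed before review. No section hides the index drug, prescriptions, INR results or cohort from the reviewer.

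On what the record holds, Section 9.4 states: "Prescriptions issued by the PCP are recorded electronically and the indication can be ascertained by reviewing the patient's clinical history". The same section lists laboratory results and free text. Section 9.1 uses warfarin-monitoring codes and INR values to establish previous use. Section 9.7.1 states: "Manual review of patient profiles will be used to ascertain as accurately as possible exposure time in a random sample of warfarin users".

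Section 9.3.2.1 requires, among other criteria for gastrointestinal bleeding, "the lesion type being NOT related to cancer". Section 9.3.2.2 asks whether an other-bleeding event came before the admission, and whether a liver case is free of several competing causes.

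**The concern.** A reviewer who can see the study drug may accept an ambiguous case more readily in one cohort than in the other. The cohort rate ratios of Section 9.7.2 and the nested case-control analyses would both inherit that difference. More person-time does not reduce it, and adjustment for baseline covariates is not designed to.

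The protocol takes differential misclassification seriously elsewhere. Of the limit to hospitalized or referred bleeds, Section 9.3.2 says: "This restriction is needed to minimize differential misclassification caused by the variability in patients' behavior in seeking care for less severe bleedings". It also warns that "the physicians' attitude towards recording these events may differ between new drugs and standard of care". Those remarks concern how events come to be recorded. The study's own acceptance step comes later and has no corresponding safeguard. The ENCePP checklist in Annex 2 marks discussion of information biases as not applicable.

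**Working it through.** **1. Does the reviewed material carry exposure?** Section 9.4 places prescriptions, laboratory results and free text in the THIN record. Section 9.7.1 has patient profiles read by hand to establish warfarin exposure time. A profile that has lost only identifying details would therefore still show the drug. This is an inference, because the protocol does not list the contents of the outcome-review extract.

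**2. Does review decide anything?** The Annex 3 lists are broad and contain codes that cannot by themselves be an incident bleed:
- Table 4: family history of subarachnoid haemorrhage, and sequelae of earlier haemorrhage.
- Table 5: a negative occult-blood test on vomit, and oesophageal varices without bleeding.
- Table 6: a history of haematuria.

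Potential cases must therefore be rejected as well as confirmed.

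**3. Where is judgement needed?**
- More: gastrointestinal site, lesion type and link to cancer; bleeding before or during the hospital stay; exclusion of other liver causes; rejection of history and non-bleeding codes.
- Less: intracranial haemorrhage, which needs imaging, lumbar puncture or a therapeutic procedure; and the bare fact of admission or referral.

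**4. Would masking cost a criterion?** No case definition in Sections 9.3.2.1 to 9.3.2.3 uses study-drug information.

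**5. Illustration of size (assumed proportions).** Suppose the true rates are equal and masked review would accept 60% of potential cases in both cohorts. If only rivaroxaban acceptance shifts, observed ratio = true ratio × (rivaroxaban acceptance ÷ comparator acceptance):
- 5 points up or down: 65/60 = 1.08; 55/60 = 0.92.
- 10 points up or down: 70/60 = 1.17; 50/60 = 0.83.

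**6. The same mechanism on the plan's own study size.** Section 9.5 plans 12,000 and 48,000 person-years, "based on an incidence of haemorrhagic stroke in warfarin-treated patients of 5 per 1000 person-years", to exclude a ratio of 1.5 with 80% power. Alpha is not stated; two-sided 0.05 is assumed.
- Expected events: 0.005 × 12,000 = 60 and 0.005 × 48,000 = 240.
- SE = √(1/60 + 1/240) = 0.144. Power = Φ(ln 1.5/0.144 − 1.96) = 80.2%, which reproduces the plan.

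Now treat 60 and 240 as true cases, assume a proportion of them is accepted and assume no false ones are:
- 85% in both: 51 and 204 events, no bias, power 73.6%.
- 90% rivaroxaban, 80% warfarin: 54 and 192 events. A true ratio of 1.0 appears as 0.90/0.80 = 1.125. SE = 0.154; power = Φ(ln(1.5/1.125)/0.154 − 1.96) = 46.3%.
- 80% rivaroxaban, 90% warfarin, true ratio 1.5: 90 × 0.80 = 72 and 216 events. The ratio appears as 1.5 × 0.80/0.90 = 1.33. SE = 0.136; the chance of wrongly excluding 1.5 is Φ(ln(1.5/1.333)/0.136 − 1.96) = 13.7%, against 2.5% without bias.

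Step 6 shows scale only. It uses haemorrhagic stroke because that is the only outcome with a stated rate, and this outcome is among those least open to reviewer judgement.

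**The case against.** The strongest reply is that the protocol is silent, not wrong. It does not say that identity is the only thing removed, or that reviewers see the drug. Prescriptions being in THIN does not prove that they are in the review extract, and the reading of warfarin profiles in Section 9.7.1 is a separate exercise on a random sample. This is fair as to wording: exposure-aware review is an inference. But both sections do specify how profiles are prepared, and a team following them exactly would have no instruction to mask the drug.

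Profiles are also reviewed only where suitable, several criteria are fairly objective, and HES offers a cross-check in some practices. This narrows the concern. It does not remove it for gastrointestinal bleeding or for the codes that must be rejected on reading.

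A reader might go further and infer any of the following, which the protocol does not support:
- That it contradicts itself by naming a bias and then committing it. Its stated worry is care-seeking and recording by physicians, which is a different mechanism from assessor bias.
- That all three primary rate ratios are biased. Nothing shows that acceptance differs by drug, and the room for judgement varies by outcome.
- That the cause-of-death review in Section 9.3.2.4 is affected in a way that matters. The objective in Section 8.2 is all-cause mortality, and Section 9.7.2 plans no cause-specific comparison.

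Finally, masking is incomplete. The primary care practitioner who answers the questionnaire knows the drug, and narrative text is hard to clean. That limits what the remedy can achieve.

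**Conclusion.** The point holds as a design weakness that is cheap to reduce. As written, case review is de-identified but not masked to exposure, and acceptance could differ by cohort where judgement enters. It should be corrected, but bias has not been shown.

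The size and direction of any bias cannot be derived from the protocol. The range of 0.83 to 1.17 rests wholly on an assumed 60% acceptance and a shift of 5 to 10 points in one cohort. The power figures rest on other assumed proportions and an assumed alpha. The planned study size itself reproduces and needs no change on this account.

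**What to change.** In Sections 9.3.2 and 9.8, state that:
- before review, a program masks anticoagulant and study-antiplatelet prescriptions, INR and anticoagulation-monitoring entries, and drug names in free text;
- the same masking is applied to returned questionnaires and copied records before the study reviewer sees them;
- case status is locked before exposure is merged in;
- the proportion of potential cases accepted is reported by cohort, for each outcome.

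The cost is a filter on the extracted material, its testing on free text, handling of returned documents, and a few sentences of protocol text. No extra reader is needed. The downsides are that free-text masking is imperfect, some clinical context for the bleed may be lost, and the practitioner's own answers remain exposure-aware. Reporting acceptance by cohort makes a remaining difference visible, although such a difference could also reflect the mix of potential cases.

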761Jy00	Other specified operation on gastric ulcer
761Jz00	Operation on gastric ulcer nos
7627	Operations on duodenal ulcer
7627100	Suture of duodenal ulcer not elsewhere classified
7627y00	Other specified operation on duodenal ulcer
7627z00	Operation on duodenal ulcer nos
G850.00	Oesophageal varices with bleeding
G852000	Oesophageal varices with bleeding in diseases EC
G852100	Oesophageal varices without bleeding in diseases EC
J10y000	Haemorrhage of oesophagus
J107.00	Mallory-Weiss syndrome
J108.00	Mallory - Weiss tear
J573.00	Haemorrhage of rectum and anus
J573000	Rectal haemorrhage
J573011	Rectal bleeding
J573012	PRB - Rectal bleeding
J573100	Anal haemorrhage
J573.11	Bleeding PR
J573z00	Haemorrhage of rectum and anus NOS
J510900	Bleeding diverticulosis
J573.00	Haemorrhage of rectum and anus
J573000	Rectal haemorrhage

C/O, complaint of; EC, elsewhere classified; GIB; gastrointestinal bleeding; H/O, history of; LOC, loss of consciousness; O/E, on examination; NEC, not elsewhere classified; NOS, not otherwise specified; PR, per rectum; PRB, per rectal bleeding.

Table 6. Read codes for urogenital bleeding.

Read code	Description
14D5.00	H/O: haematuria
1A45.00	Blood in urine - haematuria
1A45.12	Haematuria - symptom
K032100	Recurrent benign haematuria syndrome
K0A2.00	Recurrent and persistent haematuria
K0A2000	Recurrent+persistnt haematuria minor glomerular abnormality
K0A2100	Recur+persist haematuria
K0A2200	Recur+persist haematuria difus membranous glomerulonephritis
K0A2300	Recur+persist haemuria df mesangial prolif glomerulonephritis
K0A2400	Recur+persist haemuria df endocaply prolifrtv glomeruloneph
K0A2500	Recur+persist hmuria df mesangiocapillary glomerulonephritis
K0A2600	Recurrent and persistent haematuria
K0A2700	Recur+persist haematuria difus crescentic glomerulonephritis
K197.00	Haematuria
K197.11	Traumatic haematuria
K197.12	Essential haematuria
K197000	Painless haematuria
K197100	Painful haematuria
K197200	Microscopic haematuria
K197300	Frank haematuria
K197400	Clot haematuria
K53y600	Haematosalpinx
K544.00	Haematometra
K595.11	Intermenstrual bleeding - regular
K596.00	Metrorrhagia
K596.11	Intermenstrual bleeding - irregular
K597.00	Postcoital bleeding
K59A.00	Premenopausal postcoital bleeding
K59B.00	Postmenopausal postcoital bleeding
K59y.11	Metropathia haemorrhagica
K59y000	Retained menstruation
K59yx00	Dysfunctional uterine haemorrhage NOS
K59yx11	Dysfunctional uterine bleeding
K59yy00	Functional uterine haemorrhage NOS

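### The urogenital bleeding definition gives no ground to reject referred microscopic or glomerular haematuria, so such findings can count as primary safety events

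*Protocol*

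**What the plan says.** Section 9.3.2 sets one threshold for all bleeding outcomes: "clinically relevant bleedings will be defined as bleedings leading to hospital admission or referrals to a specialist". It gives the reason: "This restriction is needed to minimize differential misclassification caused by the variability in patients' behavior in seeking care for less severe bleedings". It adds that physicians may record these events differently for a new drug than for standard of care.

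For urogenital bleeding, section 9.3.2.1 states: "A patient will have to meet both of the following criteria to be considered a case of urogenital bleeding". The criteria are "the specific site of bleeding originating in the urogenital tract" and "the patient having been referred to a specialist or admitted to hospital". Nothing is said about visibility or cause.

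Annex 3, Table 6 lists the codes that find candidates. They include "Microscopic haematuria" (K197200), recurrent benign haematuria syndrome (K032100) and the nine-code block K0A2.00 to K0A2700, for example "Recur+persist haematuria difus membranous glomerulonephritis" (K0A2200).

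Sections 9.3.2 and 9.8 treat coded patients as potential cases. Profiles are reviewed where appropriate, and records are confirmed where possible, including by questionnaire to the primary care practitioner. Under section 9.7.2.1 each of the three primary outcomes has its own rate ratio.

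**The concern.** Microscopic haematuria is by its nature not seen by the patient. It comes to light when urine is tested, and referral can follow from the result. Haematuria with a named glomerular lesion is a sign of kidney disease. Both satisfy the two written criteria as soon as a referral is made, so review against those criteria cannot remove them.

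Two effects follow for a primary safety outcome. If these events occur equally in both cohorts, they pull the ratio towards 1 and can mask an excess of bleeding. If urine is tested more often in one cohort, they shift the ratio without any drug effect. The second is the kind of differential misclassification that section 9.3.2 says the restriction is there to limit.

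The neighbouring definitions are tighter. Intracranial haemorrhage must be incident and tied to imaging, lumbar puncture or a procedure. Gastrointestinal bleeding excludes cancer-related lesions. Non-infective liver disease (section 9.3.2.2) excludes competing causes. Of the three primary outcomes, only urogenital bleeding has neither a confirmation criterion nor a cause criterion.

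**Working it through.** **The plan's own figure.** The protocol gives no rate, power or precision for urogenital bleeding. Its only study-size statement (section 9.5) concerns haemorrhagic stroke: 5 per 1000 person-years, with 12,000 and 48,000 patient-years. Expected events at a true ratio of 1 are 60 and 240. The standard error of the log ratio is √(1/60 + 1/240) = 0.1443. With two-sided 5% (assumed, as the protocol does not state it), power is Φ(ln 1.5/0.1443 − 1.96) = 80.2%, which matches the stated 80%. This point does not affect that figure.

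**Code count, Table 6.**
- All codes: 48. Haematuria codes: 21.
- Microscopic: K197200 (1). Benign syndrome: K032100 (1).
- K0A2 block: 9. Six name a glomerular lesion as printed (K0A2000, K0A2200, K0A2300, K0A2400, K0A2500, K0A2700). Three name none as printed (K0A2.00, K0A2100, K0A2600).
- Codes at issue as stand-alone evidence: 1 + 1 + 6 = 8.

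**Applying the written rule.** Take a patient with K197200 or K0A2200 who is referred. Site: urogenital, met. Referral: met. The patient is a case, and no further criterion exists.

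**Effect on the ratio.** Let f be the share of comparator urogenital cases of this kind, t their rate ratio (rivaroxaban to comparator) and RR the true ratio for the other cases. Then

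observed ratio = (1 − f) × RR + f × t.

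The protocol gives neither f nor t, so both are assumed.

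Equal occurrence (t = 1):

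| f | RR = 1.5 | RR = 2.0 |
|---|---|---|
| 10% | 1.45 | 1.90 |
| 30% | 1.35 | 1.70 |
| 50% | 1.25 | 1.50 |

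For example, 0.7 × 1.5 + 0.3 × 1 = 1.35.

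No drug effect (RR = 1), unequal detection:

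| f | t = 0.5 | t = 0.8 | t = 1.25 | t = 2 |
|---|---|---|---|---|
| 10% | 0.95 | 0.98 | 1.025 | 1.10 |
| 30% | 0.85 | 0.94 | 1.075 | 1.30 |
| 50% | 0.75 | 0.90 | 1.125 | 1.50 |

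If t = RR there is no bias: at f = 30%, 0.7 × 1.5 + 0.3 × 1.5 = 1.5. Dilution therefore depends on the drug having less effect on these findings than on other urogenital bleeding.

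**The case against.** **Codes only flag potential cases.** This is correct, and a reader who inferred that every coded microscopic haematuria flows straight into the analysis would be wrong. Review can remove a code that is not a current event. It has no stated ground to remove a current, referred microscopic or glomerular haematuria. That narrower gap stands.

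**Referral or admission is the severity filter.** This also stands. The protocol chose it deliberately for all bleeding, so it would be wrong to say that the urogenital outcome has no severity criterion. But referral does not separate bleeding from a urine-test result that prompted the referral.

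**The gastrointestinal contrast has limits.** The list of lesion types applies to upper gastrointestinal bleeding only. Lower gastrointestinal bleeding has just the cancer exclusion, and neither has a visibility requirement.

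**Code counts are not case shares.** A reader might note that 11 of the 21 haematuria codes are microscopic, benign-syndrome or K0A2 codes and infer that about half of the cases are non-specific. The protocol does not support this. Nine of the 11 form one block, three of those name no lesion, Table 6 has 48 codes in all, and nothing shows how often any code is used.

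**Anticoagulation may itself raise microscopic haematuria.** The protocol is silent on this. If it does, dilution shrinks, but the dependence on testing remains.

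**Adjustment.** Renal disease and prior-year healthcare use are collected (section 9.3.1), and baseline comorbidity is adjusted for where numbers permit (section 9.7.2.1). This may reduce confounding but does not take non-specific events out of the outcome. The sensitivity analyses in section 9.7.2.7 concern the start and stop of treatment, not the case definition.

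**Conclusion.** The point holds as a gap in the case definition. Eight listed codes describe microscopic, benign-syndrome or glomerular haematuria, and the two written criteria admit them once the patient is referred. K032100 is the least clear of the eight, since its printed description names neither a lesion nor microscopic detection.

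The size is unknown. With t = 1 and f between 10% and 50%, all assumed, a true 1.5 is seen as 1.45 to 1.25. It would go too far to say that the ratio is certainly diluted. Under unequal testing and no drug effect, f = 30% gives 0.85 to 1.30 as t runs from 0.5 to 2. The protocol mentions INR monitoring of warfarin users but gives no information on which cohort has more urine testing, so no direction can be claimed.

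**What to change.** - In section 9.3.2.1, exclude from urogenital bleeding any case whose only evidence is microscopic haematuria or haematuria attributed to glomerular disease.
- In Table 6, drop K197200, K032100, K0A2000, K0A2200, K0A2300, K0A2400, K0A2500 and K0A2700 as stand-alone case codes.
- Keep K0A2.00, K0A2100 and K0A2600 as triggers for profile review.
- Do not demand proof of visible bleeding for unspecified codes such as K197.00. The code cannot settle it, confirmation is promised only where possible, and true bleeds could be lost.
- Report the current broad definition as a sensitivity analysis.

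The change is to wording and the code list, with some profile review for the three trigger codes. The cost is fewer urogenital events and a wider interval. If a share f drops out of both cohorts, the standard error of the log ratio grows by 1/√(1 − f): about 5% at f = 10% (1/√0.9 = 1.05) and 20% at f = 30% (1/√0.7 = 1.20). The precision cost is therefore large only where the share of non-specific cases was large.
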